5.4.3.1.2 ELAD Treatment Duration

Subjects randomized to receive ELAD will be treated with ELAD for a minimum of 3 days (72 hours), unless discontinuation criteria are met (See [Section 3](#)). At the end of 3 days (72 hours), a total bilirubin measurement must be taken. If the total bilirubin has increased by 25% or more from the measurement within 6 hours prior to initiation of ELAD treatment, ELAD treatment must be discontinued. If the bilirubin has not increased by 25% then treatment should continue to a maximum of 5 days (120 hours) regardless of treatment interruption (see [Section 6.6](#)). Bilirubin should be measured at least 12 hours after any procedure known to artificially alter serum bilirubin (e.g. administration of PRBCs, plasma exchange).

Subjects randomized to receive ELAD treatment will also receive standard of care therapy, and will receive medical treatment in accordance with the SOC guidelines as delineated in [Section 5.4.1](#) of this protocol and those of the institution. For overall ranges of the durations of ELAD treatments from past trials (presented in hours) see the [Investigator's Brochure](#).

5.4.3.2 ***Control Treatment Start***

Subjects randomized to Control Treatment will initiate treatment in accord with the protocol-defined standards of care immediately following randomization.

The clinical, laboratory, and hemodynamic assessments will be performed at specified intervals during the study treatment period for both the ELAD and Control groups. An overview of evaluations during study treatment is presented in [Table 2](#) for Control subjects and [Table 3](#) for ELAD subjects.

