
The standard of care labs may fulfill this requirement provided they are drawn and evaluated within 6 hours prior to ELAD treatment initiation.

- If an ELAD subject fails to meet these criteria, ELAD treatment will not be initiated, the subject will continue to receive standard of care, and the subject will be excluded from the modified intent-to-treat (mITT) population.
- If a Control subject fails to meet these criteria, the subject will continue to receive standard of care, and the subject will be excluded from the mITT population.

Subjects randomized to the ELAD group will be treated with ELAD for a minimum of 3 days (72 hours).

ELAD treatment may be interrupted for a period of *less* than 6 hours then restarted with the same set of cartridges provided that, in the opinion of the Investigator, the subject remains eligible for treatment. ELAD treatment may be interrupted for a period of *more* than 6 hours but less than 72 hours, if, for example, to allow for the conduct of a diagnostic or therapeutic procedure or for management of an adverse event, or should there be a need to interrupt the use of anticoagulants. Should this circumstance arise, a new set of ELAD cartridges must be used if treatment of the subject will continue, and the subject must meet the same safety eligibility criteria as are required prior to the initiation of treatment (See [Section 5.4.2.1.1](#)).

ELAD treatment will be discontinued and will not be restarted if any of the following discontinuation criteria are met. If ELAD treatment is discontinued, subjects will receive standard of care therapy alone and be followed through Study Day 91. Discontinuation criteria include the following:

- Continued ELAD treatment is judged to be futile, defined as an increase of more than 25% in total bilirubin at 72 (+6) hours (includes clinical consideration of impact of artifactual hyperbilirubinemia) compared to the most temporal measurement of total bilirubin taken within 6 hours prior to ELAD initiation. Bilirubin measurements must be taken at least 12 hours after any procedure known to artificially alter serum bilirubin (e.g., administration of packed red blood cells, plasma exchange);
- Subject has been off treatment for more than 72 hours;
- Subject has suffered an adverse event that, in the Investigator's opinion, requires ELAD treatment to be discontinued, and/or which cannot be resolved within a period of 72 hours;

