ELAD treatment will be discontinued and will not be restarted if any of the following discontinuation criteria are met. If ELAD treatment is discontinued, subjects will receive standard of care therapy alone and be followed through Study Day 91. Discontinuation criteria include the following:

- Continued ELAD treatment is judged to be futile, defined as an increase of more than 25% in total bilirubin at 72 (+6) hours (includes clinical consideration of impact of artifactual hyperbilirubinemia) compared to the most temporal measurement of total bilirubin taken within 6 hours prior to ELAD initiation. Bilirubin measurements must be taken at least 12 hours after any procedure known to artificially alter serum bilirubin (e.g., administration of packed red blood cells, plasma exchange);
- Subject has been off treatment for more than 72 hours;
- Subject has suffered an adverse event that, in the Investigator's opinion, requires ELAD treatment to be discontinued, and/or which cannot be resolved within a period of 72 hours;
- Subject has suffered a disseminated intravascular coagulopathy (DIC) event;
- Subject develops an indication for hemodialysis;
- Subject requires an extracorporeal procedure that takes precedence over ELAD treatment;
- Subject has been treated for a maximum of 120 hours within five (5) 24-hour periods regardless of treatment interruption;
- Subject undergoes orthotopic liver transplantation;
- Subject is discharged from the hospital;
- The first set of ELAD cartridges has been replaced for any reason and the second set also requires replacement, or the subject fails safety eligibility checks for the second set;
- Subject or legally-authorized representative withdraws consent for further ELAD treatment;
- Investigator decides to stop ELAD treatment;

- ELAD System performance issues arise that cannot be resolved within a period of 72 hours;
- Subject experiences catheter-related issues that cannot be resolved within a period of 72 hours.

Note: Regarding the judgment of futility of treatment based upon increase of bilirubin by 25%, Investigators are asked to use clinical judgment in assessing artifactual hyperbilirubinemia (e.g., resulting from transfusion of packed red blood cells) before discontinuing ELAD treatment if they believe ELAD to still be capable of providing clinical benefit. A call to the Medical Monitor should be made to discuss this, should it occur.

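### Protocol 5.4.3.1.2 restates the 72-hour bilirubin stopping rule in terms that conflict with Section 3: a mandatory stop at 25% or more, with no artifact judgment, +6 hour window or Medical Monitor call

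*Protocol*

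**What the plan says.** Section 5.4.3.1.2 of the protocol governs how long ELAD is given. It requires a check on completing the minimum course: "At the end of 3 days (72 hours), a total bilirubin measurement must be taken". If total bilirubin has "increased by 25% or more from the measurement within 6 hours prior to initiation of ELAD treatment, ELAD treatment must be discontinued". The other branch follows: "If the bilirubin has not increased by 25% then treatment should continue to a maximum of 5 days (120 hours". Its only provision for artifact is a sampling rule: "Bilirubin should be measured at least 12 hours after any procedure known to artificially alter serum bilirubin". The section cites Section 3 once, in its opening sentence, as the exception to the 72-hour minimum.

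Section 3 lists the discontinuation criteria. Futility there is "defined as an increase of more than 25% in total bilirubin at 72 (+6) hours", and a parenthesis says that this "includes clinical consideration of impact of artifactual hyperbilirubinemia". The sampling rule is firmer: "Bilirubin measurements must be taken at least 12 hours after any procedure known to artificially alter serum bilirubin". A Note under the list adds that "Investigators are asked to use clinical judgment in assessing artifactual hyperbilirubinemia" before stopping a subject whom they think ELAD could still help, and asks for a call to the Medical Monitor.

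The synopsis and SAP Section 2 carry the Section 3 criterion but not the Note. Protocol Section 6.7 refers back to Section 3 for the discontinuation criteria.

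**The concern.** The futility rule itself is not in question. The difficulty is that it appears in two operative places with different content. The version in the section on treatment duration, where a site would naturally look at hour 72, is the stricter one and leaves out the safeguard.

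The case that the safeguard addresses is foreseeable. Protocol Appendix D reports that hemoglobin tended to fall after ELAD was started in earlier studies, and the Section 3 Note gives packed red cell transfusion as its example of a cause of artifact. A subject transfused late in the first 72 hours could show a rise above 25% that does not reflect failing liver function.

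Two sites could then see the same value, each follow a section of the protocol, and act differently. A site that continued under Section 3 would also be in literal breach of a mandatory sentence in 5.4.3.1.2. At stake are consistent delivery of the experimental treatment and, for an affected subject, the remainder of the course.

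**Working it through.** The plan gives no figure for this point, so the check is a comparison of texts with some simple arithmetic.

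**Side by side**

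| Element | 5.4.3.1.2 | Section 3 | Synopsis and SAP 2 |
|---|---|---|---|
| Rise that triggers a stop | 25% or more | above 25% | above 25% |
| Timing | end of 72 hours | 72 (+6) hours | 72 (+6) hours |
| Artifact considered in the criterion | no | yes | yes |
| Note: judgment before stopping, Medical Monitor call | no | yes | no |
| 12-hour sampling rule | *should* | *must* | *must* |

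**1. Threshold.** Take a pre-ELAD bilirubin of 16.0 mg/dL (the entry minimum, used here only as an illustration). A 25% rise is 16.0 × 1.25 = 20.0 mg/dL. At exactly 20.0, 5.4.3.1.2 stops treatment and Section 3 does not. Below 20.0 neither numeric threshold is met; above it both are. The threshold wording therefore matters at a single point.

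**2. Artifact.** Above 20.0 mg/dL in the same example, Section 3 still allows treatment to go on if the rise is judged artifactual. Section 5.4.3.1.2 read alone does not. This is the substantive conflict.

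**3. Does the 12-hour rule close the gap?** The latest transfusion compatible with it is:
- for a 72-hour sample (5.4.3.1.2): 72 − 12 = hour 60;
- for the end of the Section 3 window: 78 − 12 = hour 66.

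After a transfusion later than hour 60, a 72-hour sample cannot comply. After hour 66, no sample inside the Section 3 window can. What Section 3 offers such a subject is the artifact judgment and the call, and 5.4.3.1.2 contains neither.

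**4. Largest loss per subject.** 120 − 72 = 48 hours, and 48/120 = 40% of the maximum course.

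**5. Does another clause settle it?** The Section 3 reference in 5.4.3.1.2 attaches to the 72-hour minimum, not to the 25% sentence. Section 6.7 points to Section 3, which shows the intent but does not cancel a separate mandatory sentence. SAP Section 1.1 lets the SAP prevail over the protocol only for conflicts of analysis, not for bedside decisions.

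**6. Analysis populations.** ITT keeps every randomized subject in the assigned group whatever treatment was given. The per-protocol definitions (protocol 7.2.2.3 and SAP 3.3) exclude subjects treated beyond 3 days despite a rise above 25%, with no exception for artifact. A subject properly continued under the Section 3 Note would be excluded.

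**The case against.** The best case for leaving this alone is that the intent is already clear. Section 6.7 makes Section 3 the list of discontinuation criteria, the synopsis and SAP Section 2 agree with it, and the sponsor's ELAD Specialists run the system at every site, which limits divergence. Section 5.4.3.1.2 keeps the 12-hour rule and sets no upper time limit on the sample, so a subject transfused late could plausibly be re-sampled. Investigators may stop ELAD at their own decision in any case. A subject stopped at 72 hours has still had the protocol minimum and is not excluded from per-protocol for short treatment.

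Most of this stands as a limit on size. It does not remove the conflict: the 25% sentence is mandatory and carries no exception or cross-reference, and re-sampling is only one possible reading.

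It is also fair to say that 5.4.3.1.2 is not the only protocol text with a bare numeric rule, since the per-protocol definition in 7.2.2.3 has one too. That definition classifies subjects for a sensitivity analysis and does not direct treatment. A purely numeric exclusion is defensible there in an open-label trial.

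A reader might infer that many subjects would lose 40% of their treatment. The documents do not support that. They give no transfusion rate, no transfusion timing and no frequency of artifactual rises, and falling hemoglobin is not the same as transfusion after hour 60.

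**Conclusion.** The inconsistency is real and worth correcting. Section 5.4.3.1.2 departs from Section 3, the synopsis and SAP Section 2 on the threshold, the time window and the consideration of artifact. It also omits the judgment and call in the Section 3 Note. The artifact provisions are the part that matters; the threshold wording has effect only at exactly 25%.

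The loss is at most 48 of 120 hours per affected subject. That bound assumes that the subject would otherwise have completed the full course. The number affected is unknown and probably small.

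Two stronger readings should be resisted. One is that the primary result is compromised. The ITT population and the log-rank test do not depend on how long ELAD was given, and per-protocol is a sensitivity population. The other is that the lost hours would have changed outcome. Nothing cited here shows what hours 72 to 120 add.

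**What to change.** Replace the two 25% sentences in protocol 5.4.3.1.2 with:

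> At 72 (+6) hours, apply the futility criterion and Note in Section 3. If total bilirubin has risen by more than 25% and the rise is not judged artifactual, ELAD must be stopped. If the rise may be artifactual and the Investigator believes that ELAD can still benefit the subject, the Medical Monitor should be called before stopping. In all other cases ELAD continues, up to the 120-hour maximum, with interruptions handled as in Section 6.6.

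Three features of this wording matter. It makes the stop conditional on the judgment, so it cannot be read as compelling discontinuation whatever the judgment concludes. It keeps the call to possible artifact, as Section 3 does, and does not require one for every rise above 25%. It applies Section 3 by reference, so the stricter form of the 12-hour rule comes with it. It does not remove the clash between that rule and the window for transfusions after hour 66; there the judgment and call do the work.

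Optionally, state in protocol 7.2.2.3 and SAP 3.3 whether subjects validly continued under the Section 3 Note are excluded from per-protocol.

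The cost is two sentences replaced in one protocol section. The synopsis, Section 3 and SAP Section 2 stay as they are, and sample size, data collection and the primary analysis do not change. The per-protocol clarification would add a sentence to each document.

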5.4.3.2.1 Control Treatment Duration

Subjects randomized to the Control group receive standard of care therapy alone, and will receive medical treatment in accordance with the SOC guidelines as delineated in [Section 5.4.1](#) of this protocol and those of the institution.

5.5 EVALUATIONS WHILE ON TREATMENT

All evaluations in this section are for both ELAD and Control subjects, unless specified otherwise.

5.5.1 Daily Evaluations through End of Study Day 7

The following procedures will be performed daily through End of Study Day 7, based on 24-hour periods following the End of Study Day 1, and must be performed a minimum of 12 hours apart and, if specified, either within the defined time window or during the Study Day. Any subject discharged from the hospital prior to End of Study Day 7 must return to the study site for the End of Study Day 7 evaluation only (+2 days). It is not necessary to have outpatients return for daily assessments. There may be instances where the ELAD treatment period is delayed; therefore daily evaluations may be extended beyond End of Study Day 7. Additional eCRFs may be added in this situation. See [Table 2](#) for evaluations schedules for Control subjects and [Table 3](#) for ELAD subjects:

- Physical examination (performed by a Physician, Physician Assistant, or Nurse Practitioner if within the scope of practice for institution)
- Vital signs (blood pressure, heart rate, respiration rate, temperature)
- Encephalopathy stage [West Haven Criteria, performed by a study physician, Physician Assistant, or Nurse Practitioner if within the scope of practice for institution (Refer to [Appendix A](#))] unless subject is sedated
- Routine laboratory evaluations: BUN, creatinine, glucose, sodium, potassium, chloride, carbon dioxide (or bicarbonate), calcium, magnesium, phosphate, ALT, AST, bilirubin (total/direct), albumin, total protein, alkaline phosphatase
- Additional laboratory evaluations: ammonia, lactate, α -fetoprotein, lactate dehydrogenase (LDH)
- Complete Blood Count (CBC): white blood cell count (WBC), hematocrit, hemoglobin, and platelets
- Blood collection for outside analysis (consented subjects at participating centers only - at End of Study Days 3, 5, and 7) (See [Section 5.6.3](#))
- Blood culture samples $\times 2$ – at End of Study Day 2 and End of Study Day 4 for Control subjects, or within 6 hours prior to ELAD treatment start and Hours 48 and 96 of treatment for ELAD subjects
- Ultrafiltrate samples must be drawn as described in [Section 5.6.2](#) and [Section 5.6.4](#).
- PT, PTT, and INR (If heparin is administered, PTT will be assayed in accord with the standard anticoagulation therapy protocol at the site.)
- Pulse oximetry and FiO₂ and method of delivery (for inpatients only)
- MELD score will be autocalculated in accord with [Section 5.2.4](#)
- Adverse events will be monitored continuously from Randomization and recorded
- Concomitant procedures including concomitant blood product administration (e.g., whole blood, packed red blood cells, platelets, fresh frozen plasma,

albumin, cryoprecipitate) will be monitored continuously from Randomization and recorded

- Concomitant therapies (e.g., intubation, tracheostomy, CVVH/CVVHD, arterial line) will be monitored continuously from Randomization and recorded
- Documentation of all transfers, discharges, readmissions and admissions within or outside institution. All emergency room visits must also be documented
- For outpatients Study Day 7 only: Follow-up Dietary consult (including weight)

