5.6 LABORATORY TESTING

5.6.1 Blood Culture Samples for Microbiological Testing (ELAD and Control subjects)

Blood culture samples will be collected by the Investigator or designee to determine whether the subject's blood has become contaminated. A set of blood culture samples includes one sample to be cultured under aerobic conditions, and one sample to be cultured under anaerobic conditions.

Blood culture samples will be collected to assess for possible microbial contamination in Control subjects at the End of Study Day 2 and End of Study Day 4.

The following applies to blood culture samples collected to assess for possible microbial contamination in ELAD-treated subjects:

1. Two sets of blood culture samples (1 aerobic bottle and 1 anaerobic bottle per set) will be collected by the Investigator or designee, prior to first connection to the ELAD System, and every 48 hours of ELAD treatment (Hours 0, 48, and 96).
2. During ELAD treatment, beginning at hour 48, the two sets of blood culture samples will be collected at the same time as ultrafiltrate culture samples (See [Section 5.6.2](#)).
3. All blood culture samples will be labeled and processed as per institution policy.
4. All positive (preliminary or final) blood culture results that were collected prior to or during ELAD treatment must be brought to the attention of the Sponsor immediately:
 - a. If the ELAD Specialist is on-site, the Investigator or designee must communicate the results to the ELAD Specialist, who will be responsible for promptly reporting the results to the Medical Monitor.
- OR
- b. If the ELAD Specialist is not on-site, the Investigator or designee must communicate the results via phone or text message to the Medical Monitor.
5. The Medical Monitor will promptly review the relevant information of the positive blood culture results.

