- 6 Drawn only at End of SD2 (matched safety eligibility check) and End of SD 4.
- 7 A MELD Score will be calculated using these data (see Section 5.2.4). The MELD Score must be calculated using values obtained at the same time point, and from blood draws taken within 6 hours of each other.
- 8 Only participating sites and consented subjects; draw at Screening, Days 3, 5, 7 (and/or 24 hrs post ELAD), 14, 28, and 91. If blood draw is missed at Screening, it must be drawn before End of Study Day 2.
- 9 TLFB and mTSR obtained weekly by home visit practitioners for subjects that are outpatients only. Study staff not responsible for obtaining TLFB and mTSR.
- 10 Blood alcohol testing will be done by home visit personnel if subjects are outpatients. Study site does one Blood alcohol testing (PEth) at hospital discharge only.
- 11 AEs will be monitored continuously from after Randomization throughout Study Day 91 and recorded in the eCRFs.
- 12 Concomitant medications including concomitant blood product administration (e.g., whole blood, packed red cells, platelets, fresh frozen plasma), and concomitant therapies (e.g., intubation, tracheostomy, CVVH/CVVHD, arterial blood gas) will be monitored continuously from Randomization through Study Day 91.
- 13 Documentation of all transfers, discharges, readmissions and admissions within or outside institution. All emergency room visits must also be documented.
- 14 Dietary consultation within 72 hrs of Randomization, at discharge, and all outpatient visits (including weight).
- 15 EQ-5D-5L Quality of Life Questionnaire (Appendix C) at Day 91 and hospital discharge only.

Table 3. Schedule of Evaluations and Procedures for ELAD Subjects

Treated Subject Procedures	End of SD1 (Hr 24) ¹	ELAD Treatment					Daily on End SD2 to End SD7 ^{1, 20}	End of SD 14, 21, 28 (+ 3 days)	End of SD 63 and 91 (+ 5 days)
		Safety Eligibility (-6 Hrs to ELAD Start) ²¹	Hr 1-3 ²¹	Hr 6-10 and 14-18 ²¹	Q 24 Hr on ELAD	24 Hr Post ELAD Stop ¹ (±6 hours)			
Physical Exam ³	X					X	X	X	X
Vital Signs ⁴	X	X	X	X		X	X	X	X
Exclusion Criteria check		X ²							
Weight								X ¹⁷	X ¹⁷
Encephalopathy Stage (West Haven Criteria) ³	X					X	X	X	X
Laboratory Evaluations ⁶	X	T Bili ⁷ , Cr ⁷				X	X	X	X
CBC	X	Platelets ⁷		Platelets		X	X	X	X
PT, PTT ¹⁸ , INR	X	INR ⁷ , PTT		X		X	X	X	X
Pulse Oximetry, FiO ₂ , delivery method	X					X	X ¹⁰		
Blood culture samples (×2)		X			X ⁸				
Ultrafiltrate Cultures (×2)		X ⁵			X ⁸				

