- 13 Blood alcohol testing will be done by home visit personnel if subjects are outpatients. Study site does one Blood alcohol testing (PEth) at hospital discharge only.
- 14 AEs will be monitored continuously from Randomization throughout Study Day 91 and recorded in the eCRFs.
- 15 Concomitant medications including concomitant blood products and concomitant therapies will be monitored from Randomization through Study Day 91.
- 16 Documentation of all transfers, discharges, readmissions and admissions within or outside institution. All emergency room visits must also be documented.
- 17 Dietary consultation within 72 hrs of Randomization, at discharge, and all outpatient visits (including weight).
- 18 If heparin is administered, additional PTT's will be assayed in accord with the standard anticoagulation therapy protocol at the site.
- 19 EQ-5D-5L Quality of Life Qestionnaire ([Appendix C](#)) at Day 91 and hospital discharge only.
- 20 Additional End of Study Day Visits, beyond End of Study Day 7, will need to be added as necessary if the start of ELAD Treatment is delayed beyond the End of Study Day 3.
- 21 To be repeated if ELAD cartridges are replaced.

Table 4. Schedule of Evaluations and Procedures for Standards of Care (SOC)

Important Note: This summary table does not take the place of reading the protocol. It is essential that these SOC guidelines be read and followed for study consistency across investigative sites. All study-related procedures done prior to Randomization, if done to follow the SOC described here, must have prior subject informed consent.

Standards of Care (SOC) for Treated and Control Subjects	Screening	Randomization (Study Start) through Hospitalization	Post Hospital Discharge	Comments
Steroids	Document current and prior steroid use, and pertinent clinical indications and rationale.	Administer steroids in accord with AASLD guidelines (see Section 5.4.1.2) Full documentation of steroid administration and tapering schema must be obtained in accord with Section 5.4.1.2)	Steroid use post discharge must be monitored and recorded through End of Study Day 91	

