8.3.1.1.2 Infections post-randomization

A listing of all TESAEs of infection post-randomization by subject using the terms included in **Appendix B** will be generated. The TESAEs of infection will include the following parameters: treatment group, subject ID, AE ID, SOC/Investigator term/MEDRA Preferred Term, start date/time, and stop date/time; outcome; relationship to any of the ELAD components (VTL C3A cells, System, and Procedure); whether concomitant medications (Yes/No) were administered to treat the infection; whether steroids were administered (Yes/No) to treat the alcoholic hepatitis based on a start date between Post-randomization up to Study Day 28 (to assess risk for infection); and any action taken with ELAD (i.e., prompted discontinuation). This listing will be sorted into two sections; one section will list those subjects who have an ongoing infection at randomization and the other section will list those subjects who do not have an ongoing infection at randomization.

The total number of TESAEs of infection emerging post-randomization will be summarized by Preferred Term and treatment group.

The number of subjects with at least one TESA of infection post-randomization, the number of subjects that also had an ongoing infection at baseline or no ongoing infection at baseline, and the number of subjects with at least one TESA of infection that also had a positive blood culture that occurred during the same time period as the infection, will also be summarized in separate tables for the periods between Randomization and Study Day 7, between Study Day 8 and Study Day 14, between Study Day 15 and Study Day 28 and between Study Day 29 and Study Day 91.

8.3.1.2 *Fluid Overload/Fluid Loss*

All TESAEs of fluid overload and fluid loss that emerged following randomization up to Study Day 91 for each subject will be identified by the terms listed in [Appendix C](#).

The total number of TESAEs of fluid overload/fluid loss emerging post-randomization will be summarized by Preferred Term and treatment group.

The number of subjects with at least one TESAЕ of fluid overload/fluid loss post-randomization, will also be summarized in separate tables for the periods between Randomization and Study Day 7, between Study Day 8 and Study Day 14, between Study Day 15 and Study Day 28 and between Study Day 29 and Study Day 91.

8.3.1.3 *Bleeding*

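### More scheduled blood cultures in ELAD than in Control can bias the by-arm count of culture-positive serious infections (SAP 8.3.1.1.2) upward in ELAD

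*Protocol*

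**What the plan says.** **Control schedule.** Protocol 5.5.1 sets the Control cultures "at End of Study Day 2 and End of Study Day 4 for Control subjects". Section 5.6.1 repeats this, placing the contamination cultures "in Control subjects at the End of Study Day 2 and End of Study Day 4". Table 2, footnote 6, rules out further scheduled draws: "Drawn only at End of SD2 (matched safety eligibility check) and End of SD 4".

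**ELAD schedule.** The same sentence of 5.5.1 has the draws "within 6 hours prior to ELAD treatment start and Hours 48 and 96 of treatment for ELAD subjects", and 5.6.1 gives the same three time points. In Table 3 the safety-eligibility column includes a blood culture and carries footnote 21: "To be repeated if ELAD cartridges are replaced". Section 6.5 also repeats the pre-ELAD assessments, which include cultures, after a stop of more than 6 hours.

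**Reporting.** Section 5.6.1, in its list for ELAD-treated subjects, says that positive blood cultures "collected prior to or during ELAD treatment must be brought to the attention of the Sponsor immediately". It gives no parallel instruction for Controls.

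**Analysis.** SAP 8.3.1.1.2 counts subjects with at least one serious treatment-emergent infection event (TESAE) who "also had a positive blood culture that occurred during the same time period as the infection". The tables cover Randomization to Day 7, Days 8–14, Days 15–28 and Days 29–91. SAP section 8 makes all safety summaries by treatment group. The infection section does not restrict the count to time points that both arms share, gives no per-culture denominator, and does not split scheduled from clinically driven cultures.

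**The concern.** Infection is an adverse event of special interest in the SAP, and the device runs through a large-bore catheter and an extracorporeal circuit. If one arm is cultured more often by design, a summary that depends on culture positivity can differ between arms even when the true rates are equal. An excess in ELAD in that row would then be ambiguous between device risk and detection.

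The protocol aims for the same pre-treatment evaluation in both arms (5.4.2.2), and the SAP aligns Control to End of Study Day 2 for several other comparisons. Neither step covers the cultures taken during treatment.

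**Working it through.** The documents give no infection rate, culture-positivity rate or expected count for this row, so there is no planned figure to reproduce.

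**1. Aligning the draws.** If ELAD starts at End of Study Day 2:
- pre-start draw ↔ Control End of Study Day 2
- Hour 48 = End of Study Day 4 ↔ Control End of Study Day 4
- Hour 96 = End of Study Day 6 ↔ no Control draw

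The scheduled draws are 3 against 2 overall, 2 against 1 after treatment start, and 4 against 2 overall with one cartridge replacement. A start at End of Study Day 3 puts Hour 96 at End of Study Day 7. A start at End of Study Day 4 puts it at End of Study Day 8, in the Day 8–14 table. Table 3, footnote 20, provides for starts delayed beyond End of Study Day 3.

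**2. Any positive scheduled culture.** Let p be the chance that one draw is positive, equal in both arms and independent between draws. Then P(at least one positive in k draws) = 1 − (1 − p)^k. The values of p are assumptions.

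| p | Control, k=2 | ELAD, k=3 | Ratio | ELAD, k=4 | Ratio |
|---|---|---|---|---|---|
| 1% | 1.99% | 2.97% | 1.49 | 3.94% | 1.98 |
| 2% | 3.96% | 5.88% | 1.49 | 7.76% | 1.96 |
| 5% | 9.75% | 14.26% | 1.46 | 18.55% | 1.90 |
| 10% | 19.00% | 27.10% | 1.43 | 34.39% | 1.81 |

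After treatment start only (2 against 1), the ratio is [1 − (1 − p)²]/p = 2 − p, which is 1.99, 1.98, 1.95 and 1.90. The SAP's first period starts at Randomization, so the 3-against-2 columns are the relevant ones without cartridge replacement.

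**3. Not everyone reaches Hour 96.** Let f be the share who do.
- After start, the ratio is 1 + f(1 − p). For f = 0.5 it is 1.45 to 1.50.
- Over all scheduled draws, it is 1 + f(1 − p)²/(2 − p). For f = 0.5 it runs from 1 + 0.5 × 0.81/1.90 = 1.21 (p = 10%) to 1 + 0.5 × 0.9801/1.99 = 1.25 (p = 1%).

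**4. The row needs a serious event.** Let q be the share of surveillance positives that become a serious infection event, and r = pq. With 75 per arm (the planned group size) and everyone reaching Hour 96, the expected excess over all scheduled draws is 75·r·(1 − r)². At p = 5%:
- q = 1: 75 × 0.05 × 0.9025 = 3.4 subjects
- q = 0.5: 75 × 0.025 × 0.9506 = 1.8
- q = 0.25: 75 × 0.0125 × 0.9752 = 0.9
- q = 0: 0

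This excess in subjects shrinks with q. The row also contains infections confirmed by clinically driven cultures in both arms. To the extent that those occur equally, they pull the row's ratio toward 1.

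**5. Matched draws only.** Restricted to pre-ELAD/End of Study Day 2 and Hour 48/End of Study Day 4, k = 2 in both arms, so the ratio from scheduled looking is 1.00 at any p.

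**The case against.** A reader might infer that the count is inflated, that it is about doubled, and that device risk cannot be separated from detection. The documents do not support any of these as stated.

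- **A positive culture alone does not enter the row.** The subject must have a serious infection event. A contaminant counts only if it leads to such an event or falls alongside one. This stands, and it makes the step 2 ratios an upper bound for the row. The path stays open: Appendix B includes culture-defined terms such as bacteraemia and fungaemia, Protocol 9.2 treats prolonged hospitalization or preventive intervention as serious, and an extra scheduled culture can confirm an infection diagnosed clinically.
- **A factor of two belongs to a different window.** It needs either the period after treatment start alone or a cartridge replacement. Over the SAP's own period, the shared first draw lowers it. Positive correlation between draws from one subject would lower it further. In the other direction, Controls discharged early need not return for daily assessments and may miss the End of Study Day 4 draw.
- **Other infection summaries do not need a culture.** The TESAE counts by Preferred Term and by subject, and the survival tables in SAP 7.3.7, are touched only if a surveillance positive becomes a TESAE. SAP 8.3.1.1.2 names no test for the culture row.
- **The ELAD-only escalation rule adds little.** Serious events are reportable within 24 hours in both arms, and adverse events are monitored continuously from Randomization. The rule is a second asymmetry, but it does not decide which infections are captured.
- **Replacing the count with matched draws could hide a signal.** Hour 96 follows the longest circuit and catheter exposure of the scheduled cultures, and clinically driven cultures would also be lost. This stands and shapes the fix.

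**Conclusion.** The unequal schedule is established by the protocol text and by both schedule tables, and the SAP makes no allowance for it in the culture-positive row. The supported conclusion is that the row can be biased upward in ELAD.

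The size is not derivable from the documents. With equal, independent per-draw rates of 1% to 10%, all assumed, the ratio for any positive scheduled culture is at most about 1.4 to 1.5 over all post-randomization draws without cartridge replacement, and up to about 2 after treatment start. Both fall when subjects stop before Hour 96. The excess entering the row falls to zero as fewer positives become serious events. With a delayed start the effect can move to the Day 8–14 table.

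The finding concerns a descriptive safety row. The primary analysis of overall survival is unaffected. It is worth correcting because the correction is cheap and the row bears on a device risk of special interest.

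**What to change.** In SAP 8.3.1.1.2:

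1. Keep the planned all-culture count as the main row.
2. Add a by-arm sensitivity row that leaves out positives from the unmatched scheduled ELAD draws (Hour 96 and cartridge replacement), identified by culture date/time. Keep the matched scheduled draws and all clinically driven cultures in both arms.
3. Show scheduled and clinically driven positives separately.
4. List Hour 96 and replacement-draw positives as ELAD-only data.
5. Footnote the unequal schedule under each period table, noting that Hour 96 can fall after Day 7.

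The cost is SAP wording, one extra row and a date/time filter. Blood-culture listings are already planned in SAP 8.10. The listing fields in 8.3.1.1.2 do not record how an infection was detected, so the SAP should also state the window that classes a culture as the Hour 96 or replacement draw. No procedure in the trial changes.

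The downside is small: the sensitivity row omits cultures taken after the longest circuit exposure, so it must supplement the full count and not replace it.
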